7.5 Unscheduled Visits

Interim contacts and visits (those between regularly scheduled follow up visits) may be performed at participant's parent/LAR's request or as deemed necessary by the investigator or designee at any time during the study. Parents will be asked to bring the child to the clinic at any time between visits if they have any condition that requires medical attention. All interim contacts and visits will be documented in participant's study records and on applicable case report forms as "Unscheduled visits".

7.6 End of Trial According to the Protocol

The end of the trial is defined as the date of the last contact of the last participant in the trial, according to the trial scheme.

8 STUDY EVALUATIONS

8.1 Clinical Evaluations

Definition and Categorization of AEs

The primary objective of this study is to compare the safety and immunogenicity of the liquid formulation of ROTAVIN with already licensed vaccine ROTAVIN-M1. An AE is defined as any untoward medical occurrence in a patient or clinical investigation participant administered a pharmaceutical product, which does not necessarily have a causal relationship with this treatment. An AE can therefore be any unfavorable and unintended sign (including an abnormal laboratory finding), symptom, or disease temporally associated with the use of a medicinal product, whether or not considered related to the medicinal product. Grading of AEs is also described in this section. Included below are brief listings of specific clinical safety measurements to be made. All clinical safety evaluations must be made by a qualified clinician (physician, physician assistant, or nurse practitioner) or will be self-reported by the participant's parent/LAR. Serious adverse events may occur at any time during the study. They are defined in Section 9.9.

Specific Clinical Signs and Symptoms of Interest

All clinical signs and symptoms must be documented. Specific signs and symptoms of interest, and their date of onset/occurrence and resolution, will be solicited and recorded for all participants from the time of signing ICF until termination of participation. These are listed in Section 9.7 as Solicited Systemic Reactions.

These evaluations will be made by a clinician on Days 1, 57, and 85 if not earlier. Evaluation must be performed both prior to and after administration of study product on Days 1 and 57. Reported

signs and symptoms will be recorded by the participant's parent/LAR on Diary Card from Days 1-7 and Days 57-63 in the study.

Medical History

At enrollment, medical histories must be thoroughly reviewed with the participant's parent/LAR. The following medical conditions, in particular, will be assessed:

- Presence of diarrhea or vomiting within 72 hours of enrollment or past history of persistent diarrhea.
- Presence of fever on the day of enrollment
- Any current acute disease.
- Clinically relevant history of cardiovascular, pulmonary, hepatic, renal, gastrointestinal, hematological, endocrine, immunological, dermatological, neurological, cancer, or autoimmune disease.
- Past or current history of congenital abdominal disorders, intussusception, or abdominal surgery
- Known or suspected immunologic impairment of any kind.
- Recent vaccination history.
- Recent receipt of immune globulin or other blood products, or injected or oral corticosteroids, or other immune modulator therapy since birth.
- Hypersensitivity of any kind.
- Seizures, including history of febrile seizures, or any other neurologic disorder.
- Medications taken in the 2 months (including trade name, dosing or change in dosing, indications, start date, and termination date).

Physical Examination

General Physical Examinations

A General Physical Exam is performed on each visit and anytime it is clinically indicated according to the medical judgment of the study staff. Qualified study clinicians will conduct a physical examination of all participants. This physical examination will include the following:

- Recording of general appearance.
- Physical examination of all organ systems. This includes the following:
 - Head & Neck
 - Eyes
 - Ears, Nose & Throat
 - Skin and subcutaneous tissue
 - Neurologic examination
 - Chest auscultation
 - Examination of lymph nodes (axillary and cervical)
 - Heart auscultation
 - Abdomen palpation (to check for liver size)
 - Genitourinary

- Musculoskeletal and connective tissue
- Measurement of the following vital signs:
 - Body temperature (axillary)
 - Respiratory rate
 - Heart rate

8.2 Laboratory Evaluations

To quantitate antibody concentrations elicited by the study vaccines, a baseline blood sample will be collected from all participants at one of the two sites, before the first vaccination and four weeks after the last vaccination.

Preparation, Processing, and Transport of Specimens

Collection of Blood

Following universal precautions, clinicians and experienced nurse/phlebotomists will be trained in appropriate sample collection methods. Appropriate aseptic procedures will be employed with appropriate needles and syringes in place for sample collection procedure. Following universal precautions, a maximum of 2 ml of blood, from a peripheral vein, will be collected by an aseptic technique into serum separator tubes (SST). A maximum of 3 attempts will be made for collection of the blood sample. Sampling attempt will not be repeated in case the team is not able to collect the sample on this day. A blood sample will not be collected for participant who reported a protocol deviation which might have influenced the immune response of the participant as determined by the PI or the medical monitor.

Processing of Blood specimen

Immediately after collection, the blood specimen tube will be gently inverted 4 or 5 times, (labeled with the study participant number, the protocol number and the blood specimen number), and will be stood upright to clot for at least 30 minutes at room temperature before transport to the laboratory at room temperature for processing. The specimen will be transported to the laboratory at PPMC where it will be centrifuged within 8 hours of collection.

Division of Sera

Within 8 hours of collection, clotted blood in the tube will be centrifuged at the PPMC laboratory to obtain serum. Designated laboratory personnel at the site will aliquot the samples into two aliquots as follows:

- \circ 1st aliquot: 0.5 mL for IgA assay
- 2nd aliquot: remaining serum as backup

The study participant number, date and time of collection, blood specimen number, the date and time of division and volume of serum in each aliquot will be specified on a serologic specimen log form/ study worksheet. On this form, comments may be made on the quality of specimens (e.g., hemolyzed, contaminated, etc.).

Conditions for Transport and Storage of Sera

The two aliquots will be stored in separate areas of controlled- freezer maintained at or below - 20°C until the time of shipment to the testing laboratory. These freezers will have backup power source in case of outage on the national power grid. All handling will be done to prevent unnecessary freeze-thaw cycles (i.e., back-up samples should not be thawed unless required for testing). Temperature monitoring will be done to assure maintenance of cold chain and specimen

Confidential

quality. One aliquot will be sent to the testing laboratories (i.e., laboratory at CCHMC, Cincinnati, USA) at or below -20° C using validated packaging and temperature monitors. The testing laboratories will be responsible for testing for anti-rotavirus IgA antibodies and storing of samples till study completion.

Immunological Assays

The quantitative IgA assay is the most frequently used serologic test for determining immunologic response to rotavirus vaccination. Immunogenicity will be assessed in all participants enrolled at one of the two proposed sites. Testing will be conducted on serum samples obtained before the first vaccination and four weeks after the second vaccination using a validated ELISA assay in the selected participants. The laboratory will remain blinded to the treatment allocation to the infants being tested. Geometric mean concentration (GMC), seroconversion rate, and seropositivity rate of serum anti- rotavirus IgA antibody will be calculated and compared.

Estimation of serum IgA antibodies to rotavirus by ELISA

Serum anti-rotavirus IgA is used as a measure of immunogenicity of rotavirus vaccines. Quantification of anti-rotavirus IgA antibodies will be done by ELISA using 89-12 as the substrate and will be performed at Cincinnati Children's Hospital Medical Center (CCHMC), Cincinnati, Ohio using validated procedures. The method used is an antibody sandwich enzyme immunoassay in which plates coated with polyclonal anti-rotavirus rabbit antiserum are used to capture virus lysate and detect human serum IgA in samples using biotinylated rabbit anti-human IgA. SOP no 110: Quantitative Determination of Serum Anti-Rotavirus IgA by EIA describes the procedure to measure anti-rotavirus IgA in human samples. The quantity of specific IgA is determined by comparison of the net optical density from sample wells to a standard curve generated by a human plasma standard. Dilution corrected concentrations are reported for samples if results do not fall within the quantifiable range of the standard curve.

Biohazard containment

As blood-borne pathogens can infect through contact with contaminated needles, blood, and blood products, appropriate precautions will be employed by all personnel in shipping and handling of all specimens for this study as recommended. All biological specimens will be transported using appropriate packaging. All dangerous goods or materials, including diagnostic specimens and infectious substances, must be transported according to instructions detailed in the International Air Transport Association (IATA) Dangerous Goods Regulations. Biohazard waste will be contained according to institutional, transportation/carrier, and all other applicable regulations. All dangerous goods or materials, including diagnostic specimens and infectious substances, must be transported in the International Air Transport Association (IATA) Dangerous Goods Regulations. Biohazard waste will be transported according to institutional, transportation/carrier, and all other applicable regulations. All dangerous goods or materials, including diagnostic specimens and infectious substances, must be transported according to instructions detailed in the International Air Transport Association (IATA) Dangerous Goods Regulations. Biohazardous waste will be contained according to instructions detailed in the International Air Transport Association (IATA) Dangerous Goods Regulations. Biohazardous waste will be contained according to instructions detailed in the International Air Transport Association (IATA) Dangerous Goods Regulations. Biohazardous waste will be contained according to institutional, transportation/carrier, and all other applicable regulations.

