Strategies to maintain retention in the trial include treating them respectfully, making sure they understand the study and potential side effects, and close communication with each participant parent/LAR about how the study unfolds. Given the short duration of the trial and anticipated side effects of the study vaccines, participant withdrawal and loss of follow-up is expected to be low. To prevent delays in subject visits and lost to follow-up, the study team will ensure that valid contact details are obtained prior to enrollment so that the parents/LARs can be reminded by phone at least two day before their scheduled visit. In the event of a missed visit, the participant parent/LAR will be contacted by phone; if that fails, a home visit within 3 days of the scheduled visit will be made by the field worker. A participant who cannot be located after at least 3 documented contact efforts will be considered lost to follow-up. Efforts to contact will be classified as lost to follow-up. A participant who is not vaccinated within the window of Visit 2 may be continued in the study, vaccinated outside of the window at the discretion of the investigator, and followed up according to guidance in the protocol. These cases if any will be

considered as protocol deviations and will be notified to the IEC/IRB in the progress reports and also be included in the list of protocol deviations in the study report. Participants who discontinue after enrollment will not be replaced.

POLYVAC and PATH must be informed within 48 hours of all instances of the premature termination of a participant's participation in the trial.

If the participant develops a reaction to study vaccine which the investigator believes threatens the participant's well-being, the withdrawn participant must be treated or transferred to a treatment facility.

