12.3.3 Per Protocol population

The per-protocol population is defined as all participants in the FA population who correctly received study vaccine per randomization with no major protocol deviations that are determined to potentially interfere with the immunogenicity assessment of the study vaccines. This population will serve as the primary analysis population for all immunogenicity objectives.

Due to unpredictability of some irregularities, the criteria for exclusion of participants from the Per Protocol (PP) population will be determined and defined in the statistical analysis plan (SAP) which would be finalized before the database is locked. Review of PP exclusions will be performed on blinded data by the clinical operation team, statistician and medical monitor at PATH and POLYVAC.

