12.4.5 Handling of Dropouts and Missing Data

Missing immunogenicity data will not be imputed and will be analyzed as if they were missing randomly.

Over the whole study period, the number and percentage of participants who withdraw from the study will be provided by vaccine group. All withdrawn participant's post-randomization will be further described regarding their time to dropout and their reasons for withdrawal. For participants who withdraw from the study, their data collected before withdrawal will be analyzed under full analysis (FA) population and safety population when applicable.

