17 PROTOCOL DEVIATIONS

Any changes from protocol-specified procedures and study-related SOPs occurring during the conduct of the trial will be documented and reported as protocol violations or deviations.

A Protocol Violation is any departure from the approved protocol, trial documents or any other information relating to the conduct of the study which may affect the safety of trial participants or the study outcomes. Examples include wrong randomization or enrollment of participants that do not meet inclusion / exclusion criteria.

A Protocol Deviation is any departure from the approved protocol, trial documents or any other information relating to the conduct of the trial that does not result in harm to the trial participants and does not significantly affect the study outcomes. Examples of deviations include a protocol

visit date outside the study visit window or an isolated incident of a missed or incomplete study procedure or study evaluation. Serious or repeated protocol violations or deviations will require assessment of the root cause and implementation of corrective and preventive action plans. They may constitute grounds to interrupt the trial at a study site.

The noncompliance may be either on the part of the participant, the investigator, or the study clinic staff. As a result of any deviations, corrective actions are to be developed by the site and implemented promptly. Trial procedures shall not be changed without the consent of POLYVAC/PATH. Deviations of the protocol will be examined on an individual basis, taking into account recorded information for the reason(s) that the deviation occurred.

It is the responsibility of the site to use continuous vigilance to identify and report deviations to CRO in a timely manner after identification. If required, reports of protocol deviations must be sent to the research ethics committees overseeing the research. The PI and his/her staff are responsible for knowing and adhering to their research ethics committee's/IRB's requirements.

To limit the potential for protocol deviations, the trial site will receive training (or retraining, as necessary) on protocol implementation and will operate according to written procedures.

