7.1 Analysis Populations

Definitions of analysis populations used are:

Enrolled Population: The enrolled population is defined as all screened participants who provide informed consent and are eligible for study participation, regardless of the participant's randomization and treatment status in the study.

Full Analysis (FA) population: The full analysis population is defined as all participants in the enrolled population who were randomized, received the first dose of the study vaccination, and provided at least one evaluable serum sample. The analysis based on this population will serve as supportive results for all immunogenicity objectives.

Participants in the FA population will be analyzed "as randomized", i.e. according to the vaccine a participant was designated to receive, which may be different from the vaccine that the participant actually received.

Per Protocol (PP) population: The per-protocol population is defined as all participants in the FA population who correctly received both study vaccines per randomization with no major protocol deviations that are determined to potentially interfere with the immunogenicity assessment of the study vaccines. This population will serve as the primary analysis population for all immunogenicity objectives. The criteria for exclusion of participants from the PP population is described in Section 10, Table A2, of this SAP.

Safety population: The safety population is defined as all participants in the enrolled population who received at least one dose of study vaccination and had any safety data available.

Participants in the safety population will be analyzed as “treated”, i.e. according to the actual vaccine received at the first dose. All safety analyses will be performed using this population. The denominators for different safety endpoints may vary according to the number of participants with available data for the specific endpoint. For instance, the solicited adverse event endpoints will be based only on those who have the corresponding CRF data regardless of other safety follow-up data.

The immunogenicity primary and secondary endpoints will be performed on the PP and FA population. Safety primary and secondary endpoints will be performed on the safety population. All other baseline and safety analyses, unless stated otherwise, will be performed on the safety population.

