7.4 Missing Data

In general, all missing data will be treated as missing completely at random and no imputation will be performed.

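### Protocol 8.2 lets one person withhold a blood sample on an unlisted test, which mainly removes Day-85 values from the supportive full-analysis comparison

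*Protocol*

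**What the plan says.** **Sampling.** Protocol 8.2 (Collection of Blood) says: "A blood sample will not be collected for participant who reported a protocol deviation which might have influenced the immune response of the participant". The sentence ends by giving the decision to the PI or the medical monitor. It names no visit, no qualifying deviations and no threshold. Elsewhere sampling is unconditional: Protocol section 4 (design text and the Quang Ninh site entry) and SAP 4.1 have every infant at that site bled before dose 1 and after dose 2. Protocol 7.3 lists a draw of up to 2 mL at the final visit. Protocol 7.4 has one defined exception, for infants who miss a vaccination.

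**Deviations.** Protocol 17 defines a deviation as a departure that "does not result in harm to the trial participants and does not significantly affect the study outcomes".

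**PP, the primary immunogenicity population.** SAP 7.1 requires "no major protocol deviations that are determined to potentially interfere with the immunogenicity assessment of the study vaccines". Protocol 12.3.3 adds: "Review of PP exclusions will be performed on blinded data by the clinical operation team, statistician and medical monitor at PATH and POLYVAC". Table A2 sets the decisions. Its row 46 excludes anyone without a serological result at either timepoint, including where no sample was taken, with no data review.

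**FA, the supportive population.** An infant enters, as randomized, who "received the first dose of the study vaccination, and provided at least one evaluable serum sample" (SAP 7.1). A baseline sample alone is enough.

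**Missing values.** Protocol 12.4.5: "Missing immunogenicity data will not be imputed and will be analyzed as if they were missing randomly". SAP 7.4: "all missing data will be treated as missing completely at random and no imputation will be performed".

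**The concern.** In a non-inferiority trial, the as-randomized analysis is the check on what the PP exclusions did to the result. It can do this only if the excluded infants have an outcome. Protocol 8.2 allows the outcome to go unmeasured because someone expects the deviation to have changed it. That is the ground on which PP would exclude the infant, so FA loses data from the infants it exists to add back. The plan then handles the gap as random, although the stated reason for it is an expected effect on the outcome.

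There is also an ordering problem. PP membership is meant to follow Table A2 and a joint blinded review before lock. A decision by one person at the visit, without listed criteria, can come first and settle the matter through row 46.

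**Working it through.** **1. Which sample is affected.** The baseline sample is drawn before dose 1, so the natural reading of 8.2 is the sample after dose 2 (Day 85). If the baseline were withheld too, the infant would leave FA altogether.

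**2. The two tests side by side.** Protocol 8.2 asks whether a deviation might have influenced the immune response. The PP definition asks whether a major deviation could interfere with the immunogenicity assessment. They largely overlap. Protocol 17 does not separate them: its deviations are by definition those without a significant effect on outcomes, so a site cannot tell from it which ones meet the 8.2 test.

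**3. Tracing three infants who received both doses.**

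| Deviation | Table A2 row | Sample taken: PP; FA Day 85 | Sample withheld: PP; FA Day 85 |
|---|---|---|---|
| Dose 2 outside the window | 35, Exclude | out; value present | out; no value |
| Unapproved storage excursion | 37, case by case | decided at review; value present | out by row 46; no value |
| Fever at enrolment | 6, Include | in; value present | out by row 46; no value |

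The first line is the main effect: PP is the same either way and FA loses a value. Protocol 7.4 keeps this infant in the study ("vaccinated outside of the window at the discretion of the investigator, and followed up according to guidance in the protocol"), and row 35 removes the infant from PP only. The other two lines are the secondary effect on PP. The documents give no basis for sizing it.

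**4. How many rows.** Table A2 has 47 rows: 24 Exclude, 16 Include and 7 case by case. The 24 Exclude rows divide as follows:
- 9 eligibility rows (1, 2, 5, 9, 12, 14, 19-21);
- 10 dosing, product or prohibited-treatment rows that can occur in an infant given both doses (23-27, 32, 35, 39, 40, 47);
- 5 others (29, 33, 36, 41, 46).

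The ten are an upper count of deviation types, not of infants. Wrong-arm vials (23, 24) and damaged or expired product (25, 40) may be known only to unblinded staff. The eligibility rows are left out because Protocol 5.1.3 stops dosing when an exclusion criterion is found before dose 2. That reason does not strictly cover rows 1 and 2, which are inclusion criteria.

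**5. Power.** Inputs from Protocol 12.2: SD of log10 IgA 0.8, margin 0.5, one-sided 0.025, 250 vs 125 evaluable. A true ratio of 1 is assumed.

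SE = 0.8 × √(1/n₁ + 1/n₂). Noncentrality = log10(2)/SE = 0.301/SE. Power comes from the noncentral t with n₁ + n₂ − 2 df.

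At 250/125, SE = 0.0876 and power = 92.9%, which reproduces the stated 93%.

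Withheld samples first use the non-evaluability allowance: 450 − 375 = 75 infants. The shares below are assumed losses beyond it, equal in both arms.

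| Share of 375 lost | Evaluable | Power |
|---|---|---|
| 0 | 250/125 | 92.9% |
| 1% | 248/124 | 92.7% |
| 5% | 238/119 | 91.7% |
| 10% | 225/112 | 90.1% |

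At 222/111 (333 infants, 42 fewer than planned) power is 89.8%.

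**The case against.** Much of the opposing case stands, and it limits the point.

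- **PP is untouched by what can be counted.** All ten rows are already PP exclusions, so bleeding those infants would not change the primary analysis. A PP effect needs an Include or case-by-case row. The row 37 route is narrow: Protocol 6.1.3 and 6.4 require the sponsor's written consent before product is used after a cold-chain break, so row 37 arises only after a breach or unmonitored storage.
- **The shortfall is visible.** A reader might infer a hidden loss. Table 15 prints Day-85 observations by arm, Listing 10 shows each infant's two values, Listing 5 describes deviations, and Table 8 and Listing 7 give PP exclusion reasons. Only a separate reason for withheld samples is missing.
- **The loss is not always permanent.** The final visit has a +14-day window that row 33 accepts, so a withheld sample could still be drawn within it.
- **FA does not collapse into PP.** FA still adds late samples, infants lacking only a baseline result, and wrong-arm doses unknown to blinded staff.
- **The out-of-window example depends on judgment.** Protocol 17 uses an out-of-window visit as an example of a deviation without significant effect. Withholding the sample would go against that, although row 35 excludes the infant from PP without review. The two documents pull in different directions, and 8.2 leaves the choice open.
- **The rule has a plausible purpose.** It spares an infant a venipuncture, and the medical monitor also sits on the PP review. But FA is a planned analysis that uses the sample, the draw is already scheduled, and 8.2 lets one person decide before that review.

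**Conclusion.** The point holds as a conflict between sampling rules whose main consequence is a weaker FA check. Followed as written, Protocol 8.2 can leave FA infants without a Day-85 value for a reason tied to the expected outcome, while Protocol 12.4.5 and SAP 7.4 treat the gap as random. The effect on PP through row 46 is real in principle but secondary and unquantified.

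A reader might infer biased selection or an inflated type I error. The documents do not support that: Protocol 5.2.2 keeps the PI, PATH, POLYVAC and the CROs blinded apart from designated unblinded staff, and nothing shows differential loss between arms. Any figure for bias would rest on invented inputs. Nor is this a power problem, since power stays at 90.1% after an assumed 10% loss beyond the allowance.

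The conclusion assumes that 8.2 refers to the Day-85 sample and that the baseline sample was taken. The documents give no rate of withheld samples, so the number of infants affected is unknown and may be small. The change is still worth making because it is cheap and the data concerned are those FA needs.

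**What to change.** Delete the no-sample sentence in Protocol 8.2 for infants who received both doses. Take their scheduled Visit 3 sample, and let Table A2 and the blinded review in Protocol 12.3.3 alone decide PP membership. Give one sampling rule across Protocol sections 4, 7.3, 7.4 and 8.2 and SAP 4.1, with the missed-vaccination rule in 7.4 as a stated exception.

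If the sentence must stay, list the qualifying Table A2 rows in advance. Report samples withheld under 8.2 as a separate reason by arm in Table 8 and Listing 7, including for FA infants who lack only the Day-85 value.

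Cost: a short protocol amendment with the approvals in Protocol section 16, a matching edit to the SAP, and a draw of up to 2 mL plus an assay in a few infants who may not enter PP. No visit is added.
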